9 APPENDICES

APPENDIX A: Performance Status Criteria

ECOG Performance Status Scale					
Grade	Description				
0	Normal activity. Fully active, able to carry on all pre-disease performance without restriction.				

1	Symptoms, but ambulatory. Restricted in physically strenuous activity, but ambulatory and able to carry out work of a light or sedentary nature (eg, light housework, office work).
2	In bed < 50% of the time. Ambulatory and capable of all self-care, but unable to carry out any work activities. Up and about more than 50% of waking hours.
3	In bed >50% of the time. Capable of only limited self-care, confined to bed or chair more than 50% of waking hours.
4	100% bedridden. Completely disabled. Cannot carry on any self-care. Totally confined to bed or chair.
5	Dead.

APPENDIX B: Participant Eligibility Checklist

Protocol Title:	An open-label pilot study to evaluate the efficacy and safety of a combination treatment of Sonidegib and buparlisib for the treatment of advanced basal cell carcinomas
Protocol Number:	IRB-29839
Principal Investigator:	[name]

II. Subject Information:

Subject Name/ID:

Gender: Male Female

III. Inclusion/Exclusion Criteria

Inclusion Criteria			Supporting
	Yes	No	Documentation*

1. Age 18 years or older.		
2. Able to provide written informed consent obtained prior to any screening procedures		
3. Histologically documented diagnosis of basal cell carcinoma deemed to be locally advanced or metastatic		
4. ECOG performance status ≤ 2		
5. At least one measurable site of disease (as defined by Response Evaluation Criteria in Solid Tumors), or other disease specific response assessment criteria, as appropriate.		
State age restriction and/or gender/race-ethnic restrictions.		
6. Patients with adequate bone marrow, liver and renal function, as specified below:		
• Absolute Neutrophil Count (ANC) ≥ 1.5 x 10 ⁹ /L		
• Hemoglobin (Hgb) ≥ 9 g/dL		
• Platelets $\geq 80 \times 10^9/L$		
• Serum total bilirubin ≤ 1.5 x ULN (upper limit of normal)		
• AST and ALT ≤ 2.5 x ULN or ≤ 5 x ULN if liver metastases are present		
• Plasma creatinine phosphokinase (CK) \leq 1.5 x ULN		
• Serum creatinine ≤ 1.5 x ULN or 24-hour clearance ≥ 50 mL/min		
◆◆ CK > ULN		

Exclusion Criteria	Yes	No	Supporting Documentation*

Cohort 1 only: prior therapy with non- Sonidegib Smo Inhibitor	
2. Patients who have received prior treatment with a P13K inhibitor	
3. Patients with a known hypersensitivity to buparlisib or to its excipients	
4. Metastatic CNS tumors may participate in this trial, if the patient is ≤ 4 weeks from therapy completion (incl. radiation and/or surgery), is clinically stable at the time of study entry and is not receiving corticosteroid therapy	
5. Patients who have had major surgery within 4 weeks of initiation of study medication.	
6. Patients with concurrent uncontrolled medical conditions that may interfere with their participation in the study or potentially affect the interpretation of the study data.	
7. Patients unable to take oral drugs or with lack of physical integrity of the upper gastrointestinal tract or known malabsorption syndromes. State exclusion requirements due to co-morbid disease or incurrent illness, as needed.	

8. Patients who have neuromuscular disorders (eg, inflammatory myopathies, muscular dystrophy, amyotrophic lateral sclerosis and spinal muscular atrophy) or are on concomitant treatment with that are recognized to cause rhabdomyolysis, such as HMG CoA inhibitors (statins), clofibrate and gemfibrozil, and that cannot be discontinued at least 2 weeks prior to starting Sonidegib treatment. If it is essential that the patient stays on a statin to control hyperlididemia, only pravastatin may be used with extra caution.		
9. Patients who are planning on embarking on a new strenuous exercise regimen after initiation of study treatment. NB: Muscular activities, such as strenuous exercise, that can result in significant increases in plasma CK levels should be avoided whilst on sonidegib treatment		
10. Patients who have taken part in an experimental drug study within 4 weeks of initiating treatment with Sonidegib.		
11. Patients who are receiving other antineoplastic therapy (eg, chemotherapy, targeted therapy or radiotherapy) concurrently or within 2 weeks of starting treatment with sonidegib.		

12. Patients who are receiving treatment with medications known to be moderate and strong inhibitors or inducers of CYP3A4/5 or drugs metabolized by CYP2B6 or CYP2C9 that have narrow therapeutic index, and that cannot be discontinued before starting treatment with Sonidegib. Medications that are strong CYP3A4/5 inhibitors should be discontinued at least 7 days and strong CYP3A/5 inducers for at least 2 weeks prior to starting treatment with Sonidegib.	
13. Pregnant or nursing (lactating women, where pregnancy is defined as the state of a female after conception and until the termination of gestation, confirmed by a positive hCG laboratory test (> 5 mIU/mL).	
 14. Women of child-bearing potential, defined as all women physiologically capable of becoming pregnant, including women whose career, lifestyle, or sexual orientation precludes intercourse with a male partner and women whose partners have been sterilized by vasectomy or other means, UNLESS they are using two birth control methods. The two methods can be a double barrier method or a barrier method plus a hormonal method. Adequate barrier methods of contraception include: Diaphragm, condom (by the partner), intrauterine device (copper or hormonal), sponge or spermicide. Hormonal contraceptives include any marketed contraceptive agent that includes an estrogen and/or a progestational agent. Reliable contraception should be maintained throughout the study and for 3 months after study drug discontinuation. 	

15. Uncontrolled medical medical problems including acute or chronic liver disease, renal disease or pancreatitis, diarrhea >CTCAE grade 2, active cardiac disease, uncontrolled diabetes, chronic steroids or other immunosuppressive agents		
16. Patients who have taken herbal medications and certain fruits within 7 days prior to starting study drug. Herbal medications include, but are not limited to St. John's Wort, Kava, ephedra (ma huang), dehydroepiandrosterone (DHEA), gingko biloba, yohimbe, saw palmetto, and ginseng. Fruits include the CYP3A inhibitors Seville oranges, grapefruit, pummelos, or exotic citrus fruits.		
17. Patients who are currently treated with drugs known to be moderate and strong inhibitors or inducers of isoenzyme CYP3A, and the treatment cannot be discontinued or switched to a different medication prior to starting study drug. Please refer to Table 15 for a list of prohibited inhibitors and inducers of CYP3A (Please note that co-treatment with weak inhibitors of CYP3A is allowed).		
18. Patients who have received any continuous or intermittent small molecule therapeutics (excluding monoclonal antibodies) ≤ 5 effective half lives prior to starting study drug or who have not recovered from side effects of such therapy		
19. Use of statin drugs or other medications known to associate with rhabdomyolysis. These drugs must be discontinued at enrollment		

20. Patients who have received wide field radiotherapy ≤ 4 weeks or limited field radiation for palliation ≤ 2 weeks prior to starting study drug or who have not recovered from side effects of such therapy	
21. Patients who have undergone major surgery ≤ 2 weeks prior to starting study drug or who have not recovered from side effects of such therapy.	
22. Patients who are currently taking therapeutic doses of warfarin sodium or any other coumadin-derivative anticoagulant. Low molecular weight heparin is allowed.	
23. Known diagnosis of human immunodeficiency virus (HIV) infection, Hepatitis B or Hepatitis C	
24. History of another malignancy within 3 years, except cured basal cell carcinoma of the skin, cured squamous cell carcinoma of the skin or excised carcinoma in situ of the cervix	
 25. Patients with the following mood disorders as judged by the Investigator or a psychiatrist, or as a result of patient's mood assessment questionnaire: ♦♦ Medically documented history of or active major depressive episode, bipolar disorder (I or II), obsessive-compulsive disorder, schizophrenia, a history of suicidal attempt or ideation, or homicidal ideation (immediate risk of doing harm to others) ♦♦ ≥ CTCAE Grade 3 anxiety ♦♦ Meets the cut-off score of ≥ 12 in the PHQ-9 or a cut-off of ≥ 15 in the GAD-7 mood scale, respectively, or selects a positive response of "1, 2, or 3" to question number 9 regarding potential for suicidal thoughts in the PHQ-9 (independent of the total score of the PHQ-9) 	

26. Patients unwilling or unable to comply with the protocol.		
me presection		

IV. Statement of Eligibility

This subject is **eligible** / **ineligible** for participation in the study.

Signature:
Date:
Printed Name:

^{*}All subject files must include supporting documentation to confirm subject eligibility. The method of confirmation can include, but is not limited to, laboratory test results, radiology test results, subject self-report, and medical record review.

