The highest rate of hyperglycemia (62.0%) was reported in CBKM120C2201, a phase 2 study conducted in patients with advanced endometrial carcinoma, as this was the only study among those listed allowing the enrollment of patients with controlled diabetes mellitus. However, so far, there were only two patients that experienced a Grade 4 hyperglycemia, and they both were treated at the highest dose level (150 mg/day) in the CBKM120X2101 study. Detailed guidelines to monitor and manage patients who develop hyperglycemia are provided in the Investigator's Brochure. Specifically, with regards to appropriate concomitant medication, considering that in *vitro studies* have shown that buparlisib may inhibit insulin-stimulated glucose uptake, the first recommended approach

is to use oral anti-diabetics (eg, metformin) who increases muscle and fat glucose uptake. The addition of insulin can be considered based on the guidelines of American Diabetes Association included as reference in the current protocol.

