3.2.2 Inclusion and exclusion criteria

Patients must have baseline evaluations performed prior to the first dose of study drug and must me*et al*l inclusion and exclusion criteria. Results of all baseline evaluations, which assure that all inclusion and exclusion criteria have been satisfied, must be reviewed by the Principal Investigator or his/her designee prior to enrollment of that patient. In addition, the patient must be thoroughly informed about all aspects of the study, including the study visit schedule and required evaluations and all regulatory requirements for informed consent. The written informed consent must be obtained from the patient prior to enrollment.

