3.2.2.1 Inclusion criteria

Patients eligible for enrollment into the treatment phase of this study **must meet all** of the following criteria:

- 1. Able to understand and sign informed consent
- 2. Age \geq 18 years
- 3. ECOG performance status ≤ 2
- 4. Patients with metastatic BCC, histologic confirmation of distant BCC metastasis
- 5. Patients with metastatic disease, target lesion must be measurable using CT or MRI
- 6. Patients with locally advanced BCC are required to have disease that is considered inoperable due to significant functional compromise or to have a medical contraindication to surgery
- 7. Patients with nevoid BCC syndrome (Gorlin syndrome) may enroll in this study but must meet the criteria for locally advanced or metastatic disease listed above
- 8. **COHORT 2 ONLY**: A Smoothened inhibitor must have been previously administered as monotherapy)
- 9. Adequate bone marrow function as shown by:
 - a. ANC $\geq 1.5 \times 109/L$,
 - b. Platelets $\geq 80 \text{ x} 109/\text{L}$,
 - c. Hb > 9 g/dL or values \ge LLN for site-specific lab
- 10. Total calcium (corrected for serum albumin) within normal limits (biphosphonate use for malignant hypercalcemia control is not allowed)
- 11. Magnesium \geq the lower limit of normal
- 12. Potassium within normal limits for the institution
- 13. Alanine aminotransferase (ALT) and aspartate aminotransferase (AST) within normal range (or \leq 3.0 x upper limit of normal (ULN) if liver metastases are present)
- 14. Serum bilirubin within normal range (or ≤ 1.5 x ULN if liver metastases are present; or total bilirubin ≤ 3.0 x ULN with direct bilirubin within normal range in patients with well-documented Gilbert Syndrome)
- 15. Serum creatinine ≤ 1.5 x ULN or 24-hour clearance ≥ 50 mL/min
- 16. Serum amylase < ULN
- 17. Serum lipase ≤ ULN

- 18. Fasting plasma glucose $\leq 120 \text{ mg/dL}$ (6.7 mmol/L)
- 19. Negative serum pregnancy test within 72 hours before starting study treatment in women with childbearing potential
- 20. INR < 2

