3.2.2.2 Exclusion criteria

Patients eligible for enrollment into the treatment phase of this study **must not meet any** of the following criteria:

- 1. Patients who have received prior treatment with a P13K inhibitor
- 2. Patients with a known hypersensitivity to buparlisib or to its excipients
- 3. Patients with untreated brain metastases are excluded. However, patients with metastatic CNS tumors may participate in this trial, if the patient is > 4 weeks from therapy completion (incl. radiation and/or surgery), is clinically stable at the time of study entry and is not receiving corticosteroid therapy
- 4. Patients with acute or chronic liver, renal disease or pancreatitis
- 5. Patients with baseline creatinine kinase (CK) > upper limit of normal (ULN)
- 6. Patients with the following mood disorders as judged by the Investigator or a psychiatrist, or as a result of patient's mood assessment questionnaire:
 - •• Medically documented history of or active major depressive episode, bipolar disorder (I or II), obsessive-compulsive disorder, schizophrenia, a history of suicidal attempt or ideation, or homicidal ideation (immediate risk of doing harm to others)
 - ◆◆ ≥ CTCAE Grade 3 anxiety
 - Meets the cut-off score of ≥ 12 in the PHQ-9 or a cut-off of ≥ 15 in the GAD-7 mood scale, respectively, or selects a positive response of "1, 2, or 3" to question number 9 regarding potential for suicidal thoughts in the PHQ-9 (independent of the total score of the PHQ-9)
- 7. Patients with diarrhea \geq CTCAE Grade 2
- 8. Patient has active cardiac disease including any of the following:
 - ◆◆ Persistent Left ventricular ejection fraction (LVEF) < 50% as determined by prior Multiple Grated acquisition (MUGA) scan or echocardiogram (ECHO)
 - ◆◆ QTc > 450 msec on screening ECG (using the QTcF formula)
 - ♦♦ Angina pectoris that requires the use of anti-anginal medication
 - ◆◆ Ventricular arrhythmias except for benign premature ventricular contractions
 - ◆◆ Supraventricular and nodal arrhythmias requiring a pacemaker or not controlled with medication
 - **♦♦** Conduction abnormality requiring a pacemaker
 - ◆◆ Valvular disease with document compromise in cardiac function
 - **♦♦** Symptomatic pericarditis
- 9. Patient has a history of cardiac dysfunction including any of the following:
 - ◆◆ Myocardial infraction within the last 6 months, documented by persistent elevated cardiac enzymes or persistent regional wall abnormalities on assessment of LVEF function

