 - ◆◆ History of documented congestive heart failure (New York Heart Association functional classification III-IV)
 - **♦♦** Documented cardiomyopathy

- 10. Patient has poorly controlled diabetes mellitus (defined as HgA1c > ULM), steroid-induced diabetes mellitus or insulin dependent diabetes mellitus.
- 11. Other concurrent severe and/or uncontrolled concomitant medical conditions (eg, active or uncontrolled infection) that could cause unacceptable safety risks or compromise compliance with the protocol
- ◆◆ Significant symptomatic deterioration of lung function. If clinically indicated, pulmonary function tests including measures of predicted lung volumes, DLco, O2 saturation at rest on room air should be considered to exclude pneumonitis or pulmonary infiltrates.
- 12. Impairment of gastrointestinal (GI) function or GI disease that may significantly alter the absorption of buparlisib (eg, ulcerative diseases, uncontrolled nausea, vomiting, diarrhea, malabsorption syndrome, or small bowel resection). Patients with unresolved diarrhea will be excluded as previously indicated
- 13. Patients who have been treated with any hematopoietic colony-stimulating growth factors (eg, G-CSF, GM-CSF) ≤ 2 weeks prior to starting study drug. Erythropoietin or darbepoetin therapy, if initiated at least 2 weeks prior to enrollment, may be continued.
- 14. Patients who are currently receiving treatment with medication with a known risk to prolong the QT interval or inducing Torsades de Pointes and the treatment cannot either be discontinued or switched to a different medication prior to starting study drug. Please refer to Table 16 for a list of prohibited QT-prolonging drugs with risk of Torsades de Pointes.
- 15. Patients receiving chronic treatment with steroids or another immunosuppressive agent.
 - Note: Topical applications (eg, rash), inhaled sprays (eg, obstructive airways diseases), eye drops or local injections (eg, intr-articular) are allowed. Oral or systemic liver enzyme inhibitors such as topical antifungal creams are allowed. Patients with previously treated brain metastases, who are on stable low dose corticosteriods treatment (eg, dexamethasone 2 mg/day, predisolone 10 mg/day) for at least 14 days before start of study treatment are eligible.

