4.1.2.2 Hyperglycemia

In preclinical studies, insulin/glucose homeostasis was impacted in various species (mice, rats, dogs), as expected from the mode of action of buparlisib. In both rats and dogs, at the doses used in the 4-week studies, these effects were minimal. However, in mice treated at high doses (30 or 60 mg/kg/day) a clear induction of insulin resistance/ insensitivity was observed, without clear influence of the dose or the time point of testing.

Histopathologically, pancreas and liver showed changes which are in concordance with this activity.

Grade 4 Hyperglycemia was also observed in an ongoing phase 1a study of buparlisib in patients with solid tumors (CBKM120X2101). Therefore, no patients with uncontrolled diabetes mellitus will be enrolled in this study. In all patients, fasting plasma glucose will obtained at screening and will be monitored throughout the trial. For the treatment of glucose disturbances occurring under buparlisib treatment investigators are advised to adhere to the protocol guidelines outlined in Table 10 and as follows.

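### The signed eligibility checklist and section 4.1.2.2 bar only uncontrolled diabetes, while exclusion 10 also bars insulin-dependent and steroid-induced diabetes and sets an HbA1c limit

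*Combined protocol and SAP*

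**What the plan says.** Three places state who is kept out because of diabetes.

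- Section 3.2.2.2, exclusion 10: "Patient has poorly controlled diabetes mellitus (defined as HgA1c > ULM), steroid-induced diabetes mellitus or insulin dependent diabetes mellitus". I read ULM as the upper limit of normal.
- Appendix B, exclusion item 15, in a list that opens with uncontrolled medical problems: "active cardiac disease, uncontrolled diabetes, chronic steroids or other immunosuppressive agents".
- Section 4.1.2.2: "Therefore, no patients with uncontrolled diabetes mellitus will be enrolled in this study".

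Section 3.2.2.1 adds a glucose criterion, "18. Fasting plasma glucose", with a limit of 120 mg/dL (6.7 mmol/L). Appendix B has no such line and no HbA1c line. Table 19 schedules both measurements at screening.

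On which list governs, section 3.2.2 says: "Results of all baseline evaluations, which assure that all inclusion and exclusion criteria have been satisfied, must be reviewed by the Principal Investigator" or a designee before enrollment. Appendix B ends with its own signed statement that the subject is eligible or ineligible.

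Item 15 also covers liver disease, renal disease and pancreatitis, which exclusion 4 bars without a qualifier: "Patients with acute or chronic liver, renal disease or pancreatitis". For diarrhea, exclusion 7 starts at CTCAE Grade 2, whereas item 15 starts above Grade 2.

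**The concern.** Two stated rules give opposite answers for the same patient. Exclusion 10 has three limbs, and two of them (steroid-induced and insulin-dependent) apply whatever the degree of control. The checklist and section 4.1.2.2 reduce all three to the single word uncontrolled, which neither place defines.

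The subject matter makes this more than a drafting slip. Section 1.5.2.2.1 calls hyperglycaemia an on-target effect of buparlisib, and adverse-event frequency is a secondary variable (section 6.2). Table 10 stops study drug for a second Grade 2 glucose occurrence and for a Grade 3 value that persists on recheck. With 12 patients per cohort, admitting even one patient whom the body of the protocol excludes can visibly move both the toxicity description and the response rate.

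**Working it through.** **Step 1: apply each text to the same patients.**

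| Patient | Section 3.2.2 criteria | Appendix B item 15 | Section 4.1.2.2 |
|---|---|---|---|
| Insulin-dependent, controlled, HbA1c and fasting glucose within limits | Ineligible (exclusion 10) | No diabetes exclusion met | Not excluded |
| Steroid-induced, controlled, no longer on steroids | Ineligible (exclusion 10) | No diabetes exclusion met | Not excluded |
| Steroid-induced, still on chronic steroids | Ineligible (exclusion 10) | Caught by the chronic-steroid entry | Not excluded if controlled |
| HbA1c above the limit, judged clinically controlled | Ineligible (exclusion 10) | Depends on the reading of uncontrolled | Depends on the same reading |
| Fasting glucose above 120 mg/dL, HbA1c within the limit | Ineligible (inclusion 18) | No glucose line | Depends on the reading of uncontrolled |
| HbA1c within the limit, not insulin-dependent, not steroid-induced, fasting glucose within the limit | Not barred by any diabetes or glucose criterion | Not barred | Not excluded |

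The first two rows are plain contradictions. The fourth is mainly a missing definition. The last shows that exclusion 10 itself does not bar all controlled diabetes.

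**Step 2: does another checklist line catch the first row?** No. There is no HbA1c, fasting glucose or insulin line. Nor would inclusion 18 catch this patient, whose fasting glucose is within the limit. Only exclusion 10 does.

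**Step 3: weight of one patient.** Section 3.2.1 plans 12 per cohort. Section 6.1 puts everyone who receives at least one dose in the Full Analysis Set, and everyone dosed with one valid post-baseline safety assessment in the Safety Set. If each cohort closes at 12:

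- one patient in a cohort: 1/12 = 8.3 percentage points
- two patients in a cohort: 2/12 = 16.7 percentage points
- one patient in the whole study: 1/24 = 4.2 percentage points

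These are the most by which a cohort or study proportion can move.

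**Step 4: what Table 8 can support.** All five of its all-grade percentages reproduce from the counts. The protocol's leading figure is 31/50 = 62.0%: "The highest rate of hyperglycemia (62.0%) was reported in CBKM120C2201", with the explanation that "this was the only study among those listed allowing the enrollment of patients with controlled diabetes mellitus". The other four studies pooled give:

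- any grade: (17 + 2 + 4 + 2)/(55 + 9 + 12 + 6) = 25/82 = 30.5%; ratio 0.620/0.305 = 2.03 (95% CI 1.37 to 3.01)
- Grade 3-4: 12/50 = 24.0% against (2 + 1 + 2 + 1)/82 = 6/82 = 7.3%; ratio 3.28 (95% CI 1.31 to 8.19)

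These compare whole trial populations at 100 mg/day; the present trial uses 80 mg. The share *d* of diabetics in the endometrial study is not given. If its non-diabetics had the pooled 30.5% (assumption), the rate in its diabetics would be (0.620 − (1 − *d*) × 0.305)/*d*:

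- *d* = 100%: 62%
- *d* = 60%: 83%
- *d* = 50%: 94%
- *d* = 45%: just over 100%, which is impossible

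Below a share of about 45%, then, admitting diabetics could not by itself explain the gap on this assumption. Table 8 yields no rate for diabetics as such, and none for the groups that exclusion 10 bars.

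**The case against.** The strongest reply is that the body criteria govern. Section 3.2.2 requires every criterion to be met and baseline results to be reviewed before enrollment. Inclusion 18 limits entry of poorly controlled patients whatever item 15 says. Section 4.1.2.2 is narrative, and its word uncontrolled may be shorthand for the poorly controlled of exclusion 10. The chronic-steroid entry catches some steroid-induced cases. All of this stands and keeps the likely number of errors small. It does not remove the contradiction: for the controlled insulin-dependent patient, the body review and the signed form still give different answers.

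Several stronger readings are tempting but unsupported.

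- A reader might infer that the patients who slip through are those the protocol links to a doubled hyperglycaemia rate. The 62% belongs to a whole endometrial cancer trial that allowed controlled diabetes. Exclusion 10 does not bar controlled diabetes as such, and tumour types and dose differ.
- A reader might scale the two rates to 24 patients (24 × 0.62 = 14.9 against 24 × 0.305 = 7.3 events). That supposes the whole sample resembles one source or the other, whereas the wording affects only occasional patients. It is not an upper bound either, because the rate in diabetics is unknown and could exceed 62%.
- A reader might take any Grade 3 glucose value as ending treatment. Table 10 omits buparlisib, rechecks within 24 hours, and discontinues only if Grade 3 remains.
- A reader might conclude that item 15 admits stable chronic liver or renal disease. The opening word may or may not govern the whole list; several entries carry their own qualifier, which suggests that it does not. This is an ambiguity, not a demonstrated loosening.

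**Conclusion.** The contradiction is real. Appendix B item 15 and section 4.1.2.2 omit the insulin-dependent and steroid-induced limbs of exclusion 10 and its HbA1c definition, and no glucose line on the form closes the gap. It should be corrected.

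The likely effect is one or a few mis-enrolled patients, each worth about 8 percentage points in a cohort of 12. That size assumes that the checklist is sometimes used as the working record of eligibility, that cohorts close at 12 (section 7.1.2 allows additional enrollment), and that proportions are taken over all dosed patients. Nothing in the documents shows that such a patient has been enrolled. Table 8 may be cited only as a between-trial contrast at 100 mg where controlled diabetes was allowed. Aligning the texts would not by itself exclude controlled diabetes that is neither insulin-dependent nor steroid-induced.

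**What to change.** Settle one diabetes eligibility text and use it in exclusion 10, section 4.1.2.2 and checklist item 15. Which rule is intended is for the sponsor to decide; the passages must agree. Give diabetes its own checklist line, and add lines on which the screening HbA1c and fasting plasma glucose values are entered. The value lines alone would not be enough, because a controlled insulin-dependent patient can satisfy both limits.

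In the same edit, make clear whether the opening word of item 15 qualifies liver disease, renal disease and pancreatitis, which exclusion 4 leaves unqualified. Reconcile the diarrhea threshold too (Grade 2 and above in exclusion 7, above Grade 2 in item 15).

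The cost is a wording amendment to the affected passages. No new test is needed, since Table 19 already schedules HbA1c and fasting glucose at screening. If exclusion 10 is kept, nobody is lost whom the body of the protocol does not already exclude.
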